## **AMENDMENT HISTORY**

Amendment	CIP Version	Date Issued	Author(s) of	Details of Changes
No.	No.		Changes	
1	2.0	30/11/2018	[name], [name], [name]	
 
Updated sponsor reference number and additional contact details added for protocol signatories and sponsor representative.
 
Page numbers and sub titles added.
 
Anticipated timelines for trial have been updated.
 
Site numbers and recruitment methods clarified.
 
Reference to planned later phase trials using the device have been removed.
 
Corrections made to information on research site.
 
Participant visits and sample groups clarified. Full list of study procedures for Day 2 added. Visit flow charts put into appendices.
 
More information provided on data handling and record keeping.
 
Safety reporting methods have been clarified.
 
End of clinical investigation defined as 2 weeks after last participants' last visit (LPLV).
 

2	2.1	07/12/2018	[name], [name], [name]	
 
Manufacturer clarified.
 
Recruitment via Southern Counties Continence Forum removed.
 
Recruitment via GP surgeries as participant identification centres (PICs) clarified.
 
Fluid provisions on visit days confirmed.
 
More information provided on data analysis.
 
Safety stopping criteria added.
 
Reference to SOP-RES-017 removed.
 
Layout of protocol amended.
 

3	3.0	29/01/2019	[name], [name], [name]	
 
Statement of compliance corrected from 'Research Governance Framework' to 'UK Policy Framework for Health and Social Care Research'. Reference to applicable device regulations added.
 
References to electronic database changed to read study
 

**NHS Foundation Trust** 

				
 
database (excel spreadsheet).
 
Eligibility criteria amended to include requirement to drink 500mls in the first 2 hours of the intervention period.
 
Clinically significant adverse events that would be considered stopping criteria
 

				
 
have been added.
 
Stopping criteria amended to reflect safety cohort in group 1.
 
Ethnicity data will no longer be collected.
 
Further information provided on study design regarding safety cohort in Group 1.
 
Layout of protocol amended.
 
Abbreviations list updated.
 
Safety reporting procedure clarified.
 
Anticipated study timelines adjusted.
 
Valve fitting and reconciliation clarified.
 
Reference to trial monitoring
 

4	3.1	20/08/2010	[name],	

plan added,

Anticipated timelines for trial

7	5.1	20/08/2019	[name], [name]	
 
Anterpaced unternets for that have been updated.
 
Sponsor representative details updated.
 
Page numbering corrected.
 

#### **Statement of Compliance**

This clinical investigation will be conducted in compliance with the Clinical Investigation Plan (CIP) and applicable regulatory requirements; adhering to UK Policy Framework for Health and Social Care Research and the Medical Devices Regulations 2002 (SI 618), as amended by the Medical Devices (Amendment) Regulations 2008 (SI 2936).

This Clinical Investigation Plan (CIP) describes the clinical investigation and provides information about procedures for entering participants. Every care was taken in its drafting, but corrections or amendments may be necessary. These will be circulated to investigators within the clinical investigation. Problems relating to this clinical investigation should be referred, in the first instance, to the Chief Investigator.

## **1. ABBREVIATIONS**

AE	Adverse Event
AR	Adverse Reaction
CIB	Clinical Investigator Brochure
CIP	Clinical Investigation Plan
CRF	Case Report Form/ Clinical Research Facility
GCP	Good Clinical Practise
GP	General Practitioner
ICF	Informed Consent Form
ICH	International Conference of Harmonisation
MHRA	Medicinal Health Research Authority
NHS	National Health Service
NRES	National Research Ethics Service
PI	Principle Investigator
PIL	Participant Information Sheet
R&I	Research & Innovation
REC	Research Ethics Committee
SAE	Serious Adverse Event
SAR	Serious Adverse Reaction
SOP	Standard Operating Procedure
SUSAR	Suspected Unexpected Serious Adverse Reaction
UHS	University Hospital Southampton
USADE	Unanticipated Serious Adverse Device Effect

## 2. CLINICAL INVESTIGATION SUMMARY

Clinical Investigation Title	URINARY CATHETER 'FILL AND FLUSH' VALVE: SAFETY, EFFECTIVENESS, ACCEPTABILITY AND FEASIBILITY TRIAL			
Sponsor Reference Number	41448			
Trial Centre(s)	NIHR Clinical Research Facility, Southampton University Hospital NHS Foundation Trust, [name]			
Clinical investigation Design	'First in human' Safety and acceptability testing			
Population	Long-term indwelling urinary catheter (IDC) users			
Sample Size	16			
Planned Clinical investigation Period	Six months			
Primary Objective	To assess preliminary safety, effectiveness, reliability, comfort and user acceptability of the device with adults who have a long-term IDC.			
Primary End points	Evaluation of the effectiveness of bladder drainage (Valve Log)			
Secondary End points	Patient reported outcome measures (EQ-5D, Long-term catheter Quality of Life Questionnaire, Valve log)			
Device Name	Fill and Flush Valve (the 'valve')			
Manufacturer Name	Rainbow Medical Engineering Ltd			
Principle Intended Use	To facilitate the automatic filling and flushing of the bladder when a urinary catheter is in situ.			
Anticipated Timelines	Commence recruitment – September 2019 Commence data collection – October 2019 Complete data collection – December 2020 Complete data analysis – February 2020 Issue pilot phase report – March 2020			
	These timelines are subject to change and are dependent on securing all required approvals.			

## 3. INTRODUCTION

## 3.1 Background to the study

[figure not shown]
Indwelling urinary catheters (IDC) are a medical device designed to aid bladder drainage. They are used by male and female in-patients and community-dwellers (residential/nursing homes and private homes) of all ages. They may be temporary e.g. post operatively or following trauma for accurate measurement of urine output, or long-term / permanent for those with voiding dysfunction or incontinence not amenable to treatment or alternative forms of management. IDCs comprise a pliable, hollow tube (20-40cm for women or men respectively) usually made from latex or silicone with drainage eyes at the proximal end, a drainage channel or lumen and a connecting funnel at the distal end.

They may be 'urethral' when inserted via the urethra or 'supra-pubic' when inserted via a small tract just above the pubis; in both cases the IDC is secured in place with a balloon filled with sterile water which is inflated after insertion. They are connected to a drainage bag and/or a manual catheter valve (with or without a drainage bag attached to the valve) to allow continual drainage or periodic emptying respectively.

Over 12% of NHS patients have an IDC (1) and they can be useful devices but are commonly associated with complications such as catheter-associated urinary tract infection (CAUTI). Importantly, they are the second most common cause of nosocomial (hospital acquired) infection, leading to 2,100 deaths per annum in the UK, 225,000 infections and healthcare costs of an estimated £1billion (2). For the 90,000 long-term IDC users in the UK, device blockage is one of the most frequent and costly complications (3) and is caused by the colonisation of the catheter by urease producing bacteria leading to extensive biofilm and crystallisation (4). Blockages have the potential to lead to pyelonephritis, septicaemia and endotoxic shock (4) and cause considerable pain and distress to patients (5). A recent study of long-term catheter use in England found that 40% of patient's devices blocked at least once every three months, with 20% blocking up to three times per month (Avery et al forthcoming). The need to manage blockages rapidly requires high NHS community resource-use and is the most frequent cause of unplanned catheter care (6,7). Interventions, including the use of novel catheter materials, bacteriophage therapy, catheter maintenance solutions or behavioural modifications, have yet to reduce blockage in clinical practice.

The flow of urine through IDCs can be managed by free drainage (with an attached urine collection bag) or by the filling and emptying of the bladder using a catheter valve (generally with no urine collection bag). Catheter valves are used with IDCs in isolation or in combination with a urine drainage bag. They are typically connected at the proximal end to the IDC by insertion into the funnel end of the catheter. At the distal end they are connected to the drainage bag in a similar way. The purpose of a catheter valve is to allow the bladder to fill and empty periodically thus mimicking normal bladder physiology. A theoretical model has been proposed whereby free drainage of urine into a drainage bag promotes the development of biofilm, crystallisation and subsequent blockage, whereas the mechanism of repeatedly filling and emptying produced with the use of a valve reduces blockage. This theory has been demonstrated to be valid in laboratory models with valve regulated urine flow increasing time to blockage compared to free drainage (mean 62.6 vs 35.9 hours, p = 0.039 (8). Additionally, there is evidence that bladder filling and voiding is important in maintaining bladder health by limiting local inflammatory responses in longterm IUC users (9).

Current catheter valves are 'manual' and require the user to open the valve either routinely or in response to an 'urge to void'. Therefore a) the user must have sufficient cognitive skills to ensure safe use of the device i.e. not to allow the bladder to overfill which, long-term, can damage the upper urinary tract and b) the valve may be opened and the bladder emptied before optimum bladder filling has occurred which over time may lead to reduced bladder capacity. Manual catheter valves are used by around 18% of the long-term IDC population.

## 3.2 The 'fill and flush' valve:

The fill and flush valve (Figure 1) is an automated valve which is designed to open in response to rising bladder pressure which occurs as the bladder becomes full. The valve is situated between the IDC and the drainage bag as a manual valve would be.

A detailed description of the valve is provided in the Clinical Investigator Brochure (CIB). Manufacturer's Part Numbers are as follows:

- EM02 Low Pressure Release
- EM03 Medium Pressure Release
- EM04 High Pressure Release

There are three variants of the valve which respond to different degrees of bladder pressure. People's bladders function at different pressure levels. One of the aims of this study is to gain preliminary data on which valve variant works and under which circumstances. Pressure ranges are as follows:

Low: 22 - 49cm H2O Medium: 35 - 61cm H2O High: 53 - 79cm H2O

Figure 1 Fill and Flush Valve

This valve is not currently CE marked and therefore an application has been made to the Medicines and Healthcare products Regulatory Agency (MHRA) for a Notice of No Objection to use it in this research study. The valve has shown promise for bladder drainage in preliminary laboratory studies using an experimental urinary tract (see section 3.5).

## 3.3 Intended Purpose and proof of concept:

It is intended that the automated valve will open, allowing urine to drain from the bladder in response to rising bladder pressure without the user needing the dexterity to open a manual valve. The intended population are long-term catheter users who are unable to use a manual valve but want the anticipated benefits of a 'fill and flush' mechanism. The valve will attach to the external end of the catheter, with a drainage bag attached to the other end of the valve.

## 3.4 Risks and Benefits

It is hypothesised that the benefit of the valve is this could overcome the problems cited above by ensuring optimal bladder filling followed by swift urine drainage and flushing of the catheter and drainage bag lumen thereby also reducing the risk of biofilm formation and blockage.

The potential risk is that the valve will not open or will not fully drain the bladder. This risk will be mitigated by only recruiting participants who have bladder sensation and who can report any discomfort, by scanning the bladder hourly to check the volume of urine has not risen above acceptable levels and by removing the valve should any problems occur.

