## 6.1 Adverse event (AE) recording & reporting:

For purposes of this protocol:

- All AEs will be recorded at participant visits or ad hoc phone calls with the participant and the research nurse and categorised as to expectedness, relatedness and severity.
- All non-solicited AEs will be reported. Depending on the nature of the event, the reporting procedures below should be followed. Any questions concerning adverse event reporting will be directed to the Chief Investigator in the first instance.
  - o Adverse Events form is sent to the Chief Investigator
  - Severity of AEs will be graded on a three-point scale (mild, moderate, and severe).
  - Relation (causality) and seriousness of the AE to the treatment will be assessed by the Chief Investigator.

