#### 6.1.1 Definitions of Solicited AEs:

The adverse event (AE) most likely to occur in this study is bladder discomfort. This is a study outcome and therefore will not be reported. Other potential AEs are listed in Table 2. As with bladder discomfort these AEs will be recorded but not reported.

Relationship	Description
POSSIBLE	Urinary leakage
POSSIBLE	Bladder discomfort
POSSIBLE	Catheter blockage
POSSIBLE	Haematuria
POSSIBLE	Accidental Removal
Yes	Valve not opening

[figure not shown]
Table 2 Solicited Adverse Events (AEs)

6.1.2 Specific actions following Adverse Events:

Participant advised to stop using the valve:

- If symptoms suggest a urinary tract infection advise the participant to send a urine sample to their GP
- Participant reverts to usual form of urinary catheter
  - URINARY CATHETER 'FILL AND FLUSH' VALVE: SAFETY, EFFECTIVENESS, ACCEPTABILITY AND FEASIBILITY TRIAL Protocol Version 3.1 20/08/2019 - IRAS: 245818 - ERGO: 41448

• If symptom recurs, participant to be withdrawn

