#### 6.2 Serious Adverse event (SAE) recording & reporting

For purposes of this protocol:

- All SAEs will be recorded throughout the duration of the trial until two weeks after the participant completes the study.
- All non-solicited SAEs during study participation will be reported to the Chief Investigator within 24 hours of the research nurse learning of its occurrence using an Adverse Events form. In the case of incomplete information at the time of initial reporting, all appropriate information should be provided as follow-up as soon as this becomes available.
- Relationship of the SAE to study procedures will be assessed by the Chief Investigator, as should the expected or unexpected nature of the SAE.
- All non-solicited SAEs will be reported by the Chief investigator (or delegated member of the team) to the sponsor with 24 hours of becoming aware. All information is to be sent to [contact].
- Relevant ethics committees and regulatory bodies will also be notified as required.

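### Infection is not named as a risk, and non-serious adverse events after Day 2 depend on unscheduled calls, so a low infection count could not be read as absence of infection

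*Protocol*

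**What the plan says.** Section 3.1 describes indwelling catheters as "commonly associated with complications such as catheter-associated urinary tract infection (CAUTI" and attaches a national burden to infection: "leading to 2,100 deaths per annum in the UK, 225,000 infections and healthcare costs of an estimated £1billion". For long-term users, the trial population, it turns to another complication: "device blockage is one of the most frequent and costly complications".

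Section 3.4 gives the risk of the trial valve in one sentence: "The potential risk is that the valve will not open or will not fully drain the bladder". The mitigations that follow are intact bladder sensation, hourly scans and removal of the valve.

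Section 6.1.1 singles out bladder discomfort and then says "Other potential AEs are listed in Table 2". The table lists leakage, discomfort, blockage, haematuria, accidental removal and non-opening. Events in this list are recorded but not reported onward, whereas section 6.1 requires all non-solicited events to be reported. Section 6.1.2 then provides for infection: "If symptoms suggest a urinary tract infection advise the participant to send a urine sample to their GP". It does not say that the result comes back to the study.

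On timing, section 6.1 states: "All AEs will be recorded at participant visits or ad hoc phone calls with the participant and the research nurse". Section 6.2 states: "All SAEs will be recorded throughout the duration of the trial until two weeks after the participant completes the study". Section 5.1 gives each participant two visits. Section 7.7 ends the investigation two weeks after the last participant's last visit and says that this matches the study's safety reporting.

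**The concern.** This is a first-in-human study, and its second research question (section 4.1) is whether the valve empties the bladder safely. Infection is a harm that can appear days after exposure. Each test day the drainage line is opened to fit a trial valve, possibly to swap variants, and again to restore the usual device. Used valves are cultured and examined for biofilm, but the protocol schedules no question to the participant about infection.

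If a participant develops symptoms after Day 2 and sees the GP, the event is an ordinary adverse event. It falls outside the serious-event window and after the last planned contact. The interim safety report on the first four participants and the final report could then show few or no infections, and nobody could tell whether there were few or whether nobody had asked.

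**Working it through.** The protocol gives no infection rate and no calculation behind the 16, so there is no figure to reproduce. The check is mainly a comparison of sections; the arithmetic only gives scale.

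**1. Recording periods**

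| Event | Where recorded | Stated end |
|---|---|---|
| Serious adverse event (6.2) | Throughout the trial | Two weeks after the participant completes |
| Non-serious adverse event (6.1) | Two visits, or an unscheduled call | None stated |
| End of investigation (7.7) | – | Two weeks after the last visit; not assigned to non-serious events |

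An infection between the visits can be picked up at Day 2, although no specific question is planned. After Day 2 only an unscheduled call remains. A participant stopped on Day 1 has no further testing (5.6.2), so for that person Day 1 may be the last planned contact.

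**2. Exposure.** Each day has 1 to 3 valve fittings plus 1 reconnection of the usual device, that is 2 to 4 connection changes. Over two days this is 4 to 8. The protocol does not link this count to an infection risk, so it shows exposure and nothing more.

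**3. Lag.** In the laboratory work (3.5), bacteria placed in the drainage tube reached the bladder of unvalved control models at 144 h and 168 h (144/24 = 6 days, 168/24 = 7 days). In the remaining control they had not done so by 120 h. This is a glass model, not a clinical incubation time, but it shows that a delay of days is plausible on the protocol's own evidence.

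**4. Scale.** Let p be the two-week risk of a symptomatic infection and d the chance that an infection reaches the study record. Both are assumptions. With 16 independent participants:

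- expected cases = 16p
- P(at least one case) = 1 − (1 − p)^16
- P(none recorded) = (1 − pd)^16

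| p | Expected cases | P(at least one) | P(none recorded), d = 1 | d = 0.5 | d = 0.25 |
|---|---|---|---|---|---|
| 2% | 0.32 | 27.6% | 0.724 | 0.851 | 0.923 |
| 5% | 0.80 | 56.0% | 0.440 | 0.667 | 0.818 |
| 10% | 1.60 | 81.5% | 0.185 | 0.440 | 0.667 |

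The chance that infection occurred but none was recorded is P(none recorded) minus P(no case). At p = 10% this is 0.440 − 0.185 = 0.255 for d = 0.5, and 0.667 − 0.185 = 0.482 for d = 0.25.

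**5. What full capture would show.** With 0 of n observed, the exact one-sided 95% upper bound is 1 − 0.05^(1/n). For n = 16 it is 17.1%; for the four interim participants it is 52.7%.

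**The case against.** Several stronger readings are tempting, and the protocol does not support them.

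- A reader might infer that non-serious infections have no recording route and that the report would show none by default. Unscheduled calls are a route, Day 2 covers the time since Day 1, and serious infections are covered for two weeks. Zero is certain only if d = 0, which the protocol does not imply. Section 7.7 also speaks of safety reporting in general terms, though it does not assign the two weeks to non-serious events.
- A reader might infer that leaving infection off Table 2 suppresses it. The opposite holds: listed events are recorded but not reported, while an unlisted infection must be reported once known. The gap is that nobody asks.
- A reader might infer that infection is the complication the background stresses most. For long-term users it stresses blockage at least as much, and blockage is in Table 2.

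Infection is not ignored either. Current treatment for it is an exclusion, valves are supplied sterile, bacterial migration was tested in the laboratory, and all used valves are examined. The formal safety outcomes in 4.3.1 are valve opening and residual volume, and no infection rate is planned in 5.9. The investigator's brochure and the safety event templates are not to hand and may contain a prompt. The timing of the interim review relative to any two-week period is not stated.

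All of this stands, and it limits the claim. It does not remove the mismatch between the serious and non-serious recording periods, nor the missing scheduled contact after Day 2.

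**Conclusion.** The point holds as one of passive under-recording. Infection is foreseen in 6.1.2 but not named in 3.4. After Day 2, a non-serious infection reaches the study only through an unscheduled call, with no stated end date. Followed as written, the plan would yield an infection count in the interim and final reports that cannot be read as absence of infection when it is low or zero.

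The direction follows from the text; the size does not. The risks of 2%, 5% and 10% and the capture rates of one half and one quarter are assumptions, used with independence between participants. Better capture would not establish that the valve is safe with respect to infection: 0 of 16 still leaves an upper bound of about 17%, and there is no control arm. This is a worthwhile, inexpensive improvement to safety data collection, not a flaw that invalidates the study.

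**What to change.** 1. Name infection among the risks in section 3.4.
2. State in section 6.1 that all adverse events are recorded until two weeks after the participant completes or stops, and align this with 6.2 and 7.7.
3. Keep urinary tract infection as a non-solicited event that is both recorded and reported. Do not add it to Table 2 under the existing rule of 6.1.1, which would remove the reporting.
4. Add one fixed case report form question on urinary symptoms, GP contact, urine sample or antibiotic. Ask it at Day 2 for the time since Day 1, and once by phone at the end of the two weeks.
5. Tabulate the number of participants affected in the interim and final reports, together with the number who answered the closing question.

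The cost is wording in two sections, one form question and 16 short calls within a period the trial already keeps open. For the first four participants, the interim review should either wait for the closing call or state that it precedes it. Some background infections will be counted. They would be graded for relatedness like any other event, but without a control arm they cannot be separated from a valve effect.
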